#### 14.9.2. Trademarks

| Trademarks of the GlaxoSmithKline Group of Companies |
|---|
| None  |

| Trademarks not owned by the GlaxoSmithKline Group of Companies |
|---|
| SAS   |

## 14.10. Appendix 10: List of Data Displays

### 14.10.1. Data Display Numbering

The following numbering will be applied for RAP generated displays:

| Section          | Tables      | Figures      |
|------------------|-------------|--------------|
| Study Population | 1.1 to 1.16 | N/A          |
| Efficacy         | 2.1         | N/A          |
| Safety           | 3.1 to 3.24 | N/A          |
| Pharmacokinetic  | 4.1 to 4.2  | 4.11 to 4.15 |
| Section          | Listings    |              |
| ICH Listings     | 1 to 30     |              |
| Other Listings   | 31 to 39    |              |

### 14.10.2. Deliverables

| Delivery | Description                         |
|----------|-------------------------------------|
| DE       | Dose Escalation                     |
| SAC      | Final Statistical Analysis Complete |

## 14.10.3. Study Population Tables

| Study Population Tables                         |             |                      |   |                             |             |
|---|-------------|----------------------|---|-----------------------------|-------------|
| No.   | Population  | IDSL / Example Shell | Title   | Programming Notes           | Deliverable |
| Subject Disposition                      |             |                      |   |                             |             |
| 1.1.  | All Treated | ES8                  | Summary of Subject Status and Reason for Study Withdrawal                                     | ICH E3, FDAAA, EudraCT      | SAC         |
| 1.2.  | All Treated | SD4                  | Summary of Treatment Status and Reasons for Discontinuation of Study Treatment                | ICH E3                      | SAC         |
| 1.3.  | Screened    | ES6                  | Summary of Screening Status and Reasons for Screen Failure                                    | Journal Requirements        | SAC         |
| 1.4.  | Screened    | NS1                  | Summary of Number of Participant by Country and Site ID                                       | EudraCT/Clinical Operations | SAC         |
| 1.5.  | All Treated | ES11                 | Summary of Outcome of Adverse Events which Led to Study Withdrawal at Each Study Period/Phase | EudraCT                     | SAC         |
| Protocol Deviation                       |             |                      |   |                             |             |
| 1.6.  | All Treated | DV1                  | Summary of Important Protocol Deviations  | ICH E3                      | SAC         |
| Population Analysed                      |             |                      |   |                             |             |
| 1.7.  | Screened    | SP1A                 | Summary of Study Populations  | IDSL                        | SAC         |
| Demographic and Baseline Characteristics |             |                      |   |                             |             |
| 1.8.  | All Treated | DM1                  | Summary of Demographic Characteristics  | ICH E3, FDAAA, EudraCT      | SAC         |
| 1.9.  | Screened    | DM11                 | Summary of Age Ranges   | EudraCT                     | SAC         |
| Prior and Concomitant Medications        |             |                      |   |                             |             |
| 1.10.   | All Treated | MH1                  | Summary of Past Medical Conditions  | ICH E3                      | SAC         |
| 1.11.   | All Treated | MH1                  | Summary of Current Medical Conditions   | ICH E3                      | SAC         |
| 1.12.   | All Treated | CM8                  | Summary of Concomitant Medications by Ingredient  | ICH E3                      | SAC         |
| Exposure                                 |             |                      |   |                             |             |
| 1.13.   | All Treated | EX1                  | Summary of Exposure to Study Treatment  | ICH E3                      | SAC         |

| Study Population Tables        |             |                      |   |                   |             |
|--------------------------------|-------------|----------------------|---|-------------------|-------------|
| No.                            | Population  | IDSL / Example Shell | Title   | Programming Notes | Deliverable |
| Disease Characteristics |             |                      |   |                   |             |
| 1.14.                          | All Treated | DC1                  | Summary of Disease Characteristics at Initial Diagnosis | ICH E3            | SAC         |
| 1.15.                          | All Treated | DC2                  | Summary of Disease Characteristics at Screening         | ICH E3            | SAC         |
| 1.16.                          | All Treated | LA1                  | Summary of Disease Burden at Baseline                   | ICH E3            | SAC         |

**14.10.4. Efficacy Tables**

| Efficacy: Tables |             |                      |   |                   |             |
|------------------|-------------|----------------------|---|-------------------|-------------|
| No.              | Population  | IDSL / Example Shell | Title   | Programming Notes | Deliverable |
| Responses |             |                      |   |                   |             |
| 2.1.             | All Treated | RE1a                 | Summary of Best Response without Confirmation (RECIST 1.1 Criteria) |                   | SAC         |

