Telemetry	X				X								Telemetry only required for doses > 200 mg and must start at least 60 min pre-dose and be continuous for 24h post-dose. See Section 8.2.5.
Holter monitoring	X				X		X		X				Holter monitoring must start at least 60 min pre-dose and be continuous for 24h post-dose.
12-lead ECG (Triplicate)	X	X	X		X		X		X	Q1W	X		On serial PK days (Day 1, 8 and 15), triplicate ECGs will be obtained at or about the time of each PK sample collection, as described in the SRM. On other days, triplicate ECGs will be obtained pre-dose.
Laboratory Assessments (Safety) – perform assessments pre-dose on each dosing day													
Clinical Chemistry, Urinalysis and Coagulations	X				X		X		X	Q1W	X		Refer to Appendix 2 for complete list of required laboratory assessments.
Hematology	X			X	X	X	X		X	Q1W	X		Hematology twice per week for the first two weeks (see Section 2.3.1). Refer to Appendix 2 for complete list of required laboratory assessments.
Pregnancy test					X				X	Q4W	X		Perform only in women of child bearing potential (WOCBP). Pregnancy tests during intervention phase and at discontinuation may be either serum

Procedure	DLT period (Days 1-21) ³								D22 ³	Continuation ³	TDV ¹	Follow-up	Notes		
	D1 ²	D2	D3	D4	D8	D11	D15	D16							
													or urine. Final pregnancy test must be performed within 150 days after last study intervention.		
Study intervention															
Administer study drug	X			←=====Daily Dosing=====→											A dose will be administered on Day 1, no dose will be given on Day 2 or Day 3 of the first cycle, after which, daily dosing will occur through the remainder of cycle 1 and all subsequent cycles. GSK3368715 should be administered in a fasted state at approximately the same time of day (\pm 4 h), with no food for 1 hour before and 2 hours after each dose. See Section 5.3.1 for dosing instructions on serial PK days.
Efficacy Assessment															
Tumor Imaging. Must include CT Chest. Must include CT abdomen if history of documented intraabdominal disease.										Week 9 Day1 then every 8 weeks until Week 33 Day 1 and then Q16W	X		Disease assessments will be performed until disease progression. Participants who discontinue for reasons other than PD will also be followed until the start of subsequent anti-cancer intervention. CR or PR should be confirmed as per response criteria in Appendix 10 .		
Patient Reported Outcomes															

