3. OBJECTIVES AND ENDPOINTS

Objectives	Endpoints
Part 1: Dose Escalation	
Primary	

 Determine RP2D and schedule of GSK3368715 administered orally to participants with advanced stage solid tumors 	
 Incidence of DLT Incidence and severity of adverse events
Secondary	

 Evaluate the preliminary clinical activity of GSK3368715 	
 Best overall response

 Characterize the PK of GSK3368715, including the PK in the fed and fasted state in the food effect sub-study 	
 PK parameters (Cmax, Tmax, AUC, others) PK parameters (Cmax, Tmax and AUC) in the fed and fasted state in the food effect sub-study
Part 2: Dose Expansion	
Primary	

 Evaluate the preliminary clinical activity of GSK3368715 	
 Objective response rate (ORR)
Secondary	

 Characterize the safety of GSK3368715 administered at the RP2D and schedule to participants with DLBCL, pancreatic cancer, NSCLC, and bladder cancer 	
 Incidence and severity of adverse events

 Further evaluate the clinical activity of GSK3368715 	
 Progression-free survival (PFS)

 Characterize the PK of GSK3368715 	
 PK parameters (Cmax, Tmax, AUC, others)
Part 1 and Part 2	
Exploratory	

 Evaluate time to response (TTR), duration of response (DOR) and overall survival (OS) Evaluate changes in PD biomarkers relevant to define the molecular mode-of-action of GSK3368715 Investigate biomarkers such as, but not restricted to, MTAP deficiency and CDKN2A gene deletion, as potentially predictive of sensitivity or resistance to GSK3368715 Characterize the relationship between PK, PD, and clinical activity of GSK3368715 Evaluate the relationship of pharmacogenetic profile in host DNA and response to GSK3368715 therapy Determine the impact of GSK3368715 on function and health-related quality of life Determine the amount of GSK3368715 excreted in urine from participants in the 	

PK/PD expansion cohorts

- Characterize the metabolic profile of GSK3368715 (in the PK/PD expansion cohorts)

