intervention. Participants may continue treatment in the study until disease progression, unacceptable toxicity, or withdrawal of consent. For participants who discontinue intervention prior to a determination of PD, the follow-up period includes disease assessments every 8 weeks until documented PD. Following PD or for participants that discontinue study intervention, participants will be contacted every 12 weeks to assess survival status for 2 years from the start of the study. Participants with confirmed partial response (PR) or complete response (CR) will be followed for response duration.

Assessment of disease status will be performed by the Investigator in accordance with Response Evaluation Criteria in Solid Tumors (RECIST) v1.1 and the latest version of Lugano Criteria for NHL.

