8.1. Efficacy

- Disease assessment modalities may include imaging (e.g., computed tomography [CT] scan, magnetic resonance imaging [MRI], bone scan, plain radiography) and physical examination (as indicated for palpable/superficial lesions).
- The baseline disease assessment will be completed within 4 weeks prior to the first dose of GSK3368715, then after 8 weeks of dosing (week 9 day 1) and every 8 weeks thereafter until the end of week 32 then every 16 weeks, until disease progression. See the SoA (Section 1.3 Table 2) for the schedule of assessments of anticancer activity.
- Assessments must be performed on a calendar schedule and should not be affected by dose interruptions/delays.
- For post-baseline assessments, a window of ± 7 days is permitted to allow for flexible scheduling. If the last radiographic assessment was 8 weeks or more prior to the participant's withdrawal from study intervention and PD has not been documented, a disease assessment should be obtained at the time of withdrawal from the study intervention.
- Participants whose disease responds (either complete response [CR] or partial response [PR]) should have a confirmatory disease assessment performed at least 4 weeks after the date of assessment during which the response was

demonstrated. More frequent disease assessments may be performed at the discretion of the investigator.

- To ensure comparability between the baseline and subsequent assessments, the same method of assessment and the same technique will be used when assessing response.

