10.10.1.4.5. Evaluation of best overall response

The best overall response is the best response recorded from the start of the intervention until disease progression/recurrence and will be determined programmatically by GSK based on the investigators assessment of response at each time point.

- To be assigned a status of SD, follow-up disease assessment must have met the SD criteria at least once after first dose at a minimum interval of 49 days (based on the expected 56 ± 7 day window).
- If the minimum time for SD is not met, best response will depend on the subsequent assessments. For example if an assessment of PD follows the assessment of SD and SD does not meet the minimum time requirement the best response will be PD. Alternatively, participants lost to follow-up after an SD assessment not meeting the minimum time criteria will be considered not evaluable.

10.10.1.4.6. Confirmation Criteria:

- To be assigned a status of PR or CR, a confirmatory disease assessment should be performed no less than 4 weeks (28 days) after the criteria for response are first met.

10.10.2. Evaluation, Staging and Response Assessments for Non-Hodgkin's Lymphoma: The Lugano Classification (according to Cheson, 2014)

Evaluation, staging, and response criteria are summarized in 3 tables below.

Criteria for Involvement of Site

Tissue Site	Clinical	FDG Avidity	Test	Positive Finding
Lymph nodes	Palpable	FDG-avid histologies	PET-CT	Increased FDG uptake
		Non avid disease	CT	Unexplained node enlargement
Spleen	Palpable	FDG-avid histologies	PET-CT	Diffuse uptake, solitary mass, miliary lesions, nodules
		Non avid disease	CT	> 13 cm in vertical length, mass, nodules
Liver	Palpable	FDG-avid histologies	PET-CT	Diffuse uptake, mass
		Non avid disease	CT	Nodules
CNS	Signs, symptoms		CT	Mass lesion(s)
			MRI	Leptomeningeal infiltration, mass lesions
			CSF assessment	Cytology, flow cytometry
Other (eg, skin, lung, GI tract, bone, bone marrow)	Site dependent		PET-CT ^a , biopsy	Lymphoma involvement

Abbreviations: CSF, cerebrospinal fluid; CT, computed tomography; FDG, fluorodeoxyglucose; MRI, magnetic resonance imaging; PET, positron emission tomography.

a: PET-CT is adequate for determination of bone marrow involvement and can be considered highly suggestive for involvement of other extralymphatic sites. Biopsy confirmation of those sites can be considered if necessary.

Staging System for Primary Nodal Lymphomas

Stage	Involvement	Extranodal (E) Status
Limited		

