## **7. EFFICACY ANALYSES**

The Dose Escalation Committee (DEC) evaluated the DL100mg cohort and deemed it safe, but upon review of the cumulative safety, efficacy, PK and PD data, GSK decided that no further enrolment will take place on the study. As a result, all analyses corresponding to Part 2, as well as the Exploratory Objectives for both Part 1 and Part 2, will not be performed. However, all other Part 1 analyses will be performed.

Thus, only BOR for Part 1 will be summarized by treatment group: CR, PR, overall response (CR+PR), SD, PD and NE. All other planned analyses which are described below will not be performed. However, overall survival times will be listed and summarised.

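### The SAP's only efficacy table reports unconfirmed best response, while the protocol makes PR or CR conditional on a confirmatory assessment at least 28 days later, and the SAP neither declares nor justifies the change

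*SAP*

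**What the plan says.** Protocol Section 3 gives "Best overall response" as the endpoint for the Part 1 secondary objective on clinical activity. For solid tumours, Appendix 10 (10.10.1.4.6) states: "To be assigned a status of PR or CR, a confirmatory disease assessment should be performed no less than 4 weeks (28 days) after" the response criteria are first met. The Part 1 Schedule of Activities (Section 1.3, Table 2, Tumor Imaging row) says "CR or PR should be confirmed as per response criteria in" Appendix 10. Section 8.1 adds that participants who respond "should have a confirmatory disease assessment performed at least 4 weeks after the date of assessment" at which response was shown. Section 4.1 uses the same notion: "Participants with confirmed partial response (PR) or complete response (CR) will be followed for response duration".

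SAP Section 7 keeps one efficacy summary: "Thus, only BOR for Part 1 will be summarized by treatment group: CR, PR, overall response (CR+PR), SD, PD and NE". Section 7.2 adds an exact 95% confidence interval for ORR, and Section 7.2.2 names the All-Treated population. SAP 14.10.1 ("The following numbering will be applied for RAP generated displays") allots efficacy a single table number, 2.1, and no figures. SAP 14.10.4 gives that table's title: "Summary of Best Response without Confirmation (RECIST 1.1 Criteria". Listing 12 in SAP 14.10.8 is also labelled as unconfirmed. Listing 13, the listing of each subject's best response, states no basis.

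**The concern.** The protocol ties PR and CR status to confirmation, and the only planned table of that endpoint drops the condition. Protocol Section 9.6 asks that deviations from the planned analysis be documented in the analysis plan and the study report. SAP 2.1, which exists to record changes from the protocol's analysis, lists only analyses that will not be done: food effect, Part 2, RP2D and interim futility. Section 7 never mentions confirmation, and SAP 14.6.4 sends the reader back to Section 7 for endpoint derivation.

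What is at stake is the response rate that goes into the study report. If the SAP is followed as written, the only tabulated CR+PR rate and its interval may not be the protocol's quantity, and nothing in the text would alert a reader who stops at Section 7.

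**Working it through.** The plan gives no figure to reproduce, so the check has three parts: which rule governs Part 1, the direction of any difference, and its possible size.

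**1. Which rule governs Part 1**

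| Source | Basis for PR/CR |
|---|---|
| Protocol 10.10.1.4.6 (solid tumours) | Confirmed, at least 28 days later |
| Protocol 1.3, Table 2 (Part 1) | Confirmed, by reference to Appendix 10 |
| Protocol 8.1 | Confirmatory assessment for any responder, at least 4 weeks later |
| SAP 7 and 7.2 | Not stated |
| SAP Table 2.1 and Listing 12 | Unconfirmed |
| SAP Listing 13 | Not stated |

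Part 1 enrols only solid tumours (Protocol 5.1), so the solid-tumour rule covers every Part 1 participant. No planned SAP display is labelled as confirmed.

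**2. Direction**

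Every confirmed responder is also a responder when confirmation is not required. With *n* fixed (All-Treated, missing responses counted as non-response), unconfirmed rate = confirmed rate + *u*/*n*, where *u* ≥ 0 is the number of participants whose only PR or CR was never confirmed. The unconfirmed rate can equal or exceed the protocol-defined rate and cannot fall below it.

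**3. Possible size**

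Take *u* = 1 and no confirmed responders. The shift is 100/*n* percentage points. Exact (Clopper-Pearson) 95% limits for *x* responders out of *n* are the 0.025 quantile of Beta(*x*, *n*−*x*+1) and the 0.975 quantile of Beta(*x*+1, *n*−*x*), with a lower limit of 0 when *x* = 0.

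| *n* in dose group | Protocol rule, *x* = 0 | Table 2.1, *x* = 1 | Shift (points) |
|---|---|---|---|
| 3 | 0% (0 to 70.8) | 33.3% (0.8 to 90.6) | 33.3 |
| 6 | 0% (0 to 45.9) | 16.7% (0.4 to 64.1) | 16.7 |
| 12 | 0% (0 to 26.5) | 8.3% (0.2 to 38.5) | 8.3 |
| 15 | 0% (0 to 21.8) | 6.7% (0.2 to 31.9) | 6.7 |

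The group sizes are assumptions. Three and 12 are the limits on DLT-evaluable participants per dose in Protocol 4.1.1, and 6 lies between them. Fifteen is 12 plus an assumed 3 replaced participants, who would still count as All-Treated. Dose groups are used because the SAP summarises Part 1 by dose level (5.1 and 7).

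**4. Can confirmation be derived from the planned scans?**

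Protocol 1.3 and 8.1 schedule scans every 8 weeks to Week 33 and every 16 weeks afterwards, with a window of ±7 days. The smallest gap between consecutive scheduled scans is 56 − 14 = 42 days, then 112 − 14 = 98 days. Both exceed 28, so two consecutive calendar scans always meet the interval. Scans at treatment discontinuation are outside this calculation and may fall sooner.

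**The case against.** The strongest reply is that the basis is disclosed. SAP 7.2.3 refers the reader to the list of displays, where both Table 2.1 and Listing 12 carry the unconfirmed label, and Protocol 9.6 does not require the entry to sit in SAP 2.1 in particular. That is fair as far as it goes, but the cross-reference leads only to titles. It gives no reason, and it does not acknowledge that the protocol says otherwise.

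The protocol support can also be called thin. The schedule and Section 8.1 instruct sites to perform a scan, Section 4.1 concerns follow-up for duration, and the explicit definition of ORR as confirmed (9.6.1) belongs to the cancelled Part 2. Section 10.10.1.4.5 defines best overall response as the best one recorded, without mentioning confirmation, and 10.10.1.4.6 uses the word should. Much of this is accurate, and the analytic claim does rest mainly on 10.10.1.4.6. That clause, however, sets a condition for assigning the status, and the Part 1 schedule points to it. On the softest reading the SAP would still have to say which basis it takes and why.

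Finally, the effect may be nil. Enrolment has ended, the RP2D and Part 2 analyses are dropped, and the only response information given is stable disease of at least 8 weeks in 4 of 19 participants (Protocol 2.3.2). Participant-level responses and lesion measurements (Listings 12, 13 and 37) would let a reader check confirmation by hand. This limits the importance of the point. It does not make the table consistent with the protocol, and a pre-specified definition should not depend on whether responders turn up.

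**Conclusion.** The concern holds. The SAP's one efficacy table uses a response definition that differs from the protocol's, and the change is visible only in display titles, without declaration or justification. Any resulting error runs upwards: one unconfirmed response adds 1/*n* to a dose group's rate, from 6.7 points at *n* = 15 to 33.3 points at *n* = 3 for the sizes assumed here. If there is no unconfirmed PR or CR, the difference is zero; the documents do not settle which applies.

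Two limits apply. The table shell is not in the documents, so the reading rests on the title, and SAP 7.2 does not say in which display the confidence interval will appear. The endpoint is descriptive and secondary, and no decision hangs on it. It should be fixed because it alters the definition of the only efficacy result that will be tabulated.

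**What to change.** - Make confirmed best overall response under Protocol 10.10.1.4.6 the main Table 2.1, with CR+PR and its exact 95% CI by dose group in the All-Treated population.
- State in SAP Section 7 how a PR or CR that is never confirmed is classified, and how that rule works with the 49-day minimum for SD in Protocol 10.10.1.4.5.
- Keep the unconfirmed table as a supportive display labelled as such, and state the basis of Listing 13.
- Record the unconfirmed display in SAP 2.1.

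The cost is one classification rule, one derivation, one added table, one label and one line in SAP 2.1. No new data are needed, because confirmatory assessments are already required by Protocol 8.1. The price in results is that the main response rate cannot be higher than the unconfirmed one and may be lower.

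A lesser alternative is to keep the unconfirmed table alone and to declare and justify it in SAP 2.1 and Section 7. That would close the documentation gap but leave the protocol-defined rate untabulated.
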